It is necessary to monitor and record the occurrence of the adverse events and its development in detail throughout the clinical trial.

(IV) Observation index of curative effects

To record the changes in hemoglobin concentration and hematocrit before and after blood transfusion.

(V) Concomitant treatment

During the study, all concomitant treatments or combined medications (from the beginning of the signed informed consent to the end of the trial) must be recorded in detail in the original medical record, including the intervention name, intervention purpose, dosage form, single dose, dosage unit, frequency of use, route of administration, start date, end date, and whether it is still being used.

For the combined treatment in the clinical research process, the corresponding analysis and recording should be done, especially the combined treatment in the event of adverse events, recorded and reported in a timely manner.

VII. Evaluation Index

(I) Main indicators for evaluation of the effectiveness

Hemoglobin concentration and hematocrit.

(II) The indicators for evaluation of the safety of the trial

1. Incidence of anti-D alloimmunization;
2. Transfusion r adverse reaction;
3. Vital signs: temperature, heart rate, breathing, blood pressure;

4. Blood routine (WBC, NEUT, Hb, Hct, PLT), renal function (Urea, Cr), liver function (ALT, AST, TBIL, DBIL, TP, ALB), electrolytes (K^+ , Na^+ , Ca^{2+} , P^{3+} , Mg^{2+}) before and after transfusion;
5. Incidence and severity of adverse events.

VIII. Steps of Clinical trial

(I) Phase I of Visiting: -7 ~ 0 days before transfusion

1. To explain the research purpose, methods, and requirements to the subjects, and to sign the informed consent for blood transfusion treatment by the two parties jointly;
2. To Collecting the demographics, characteristics, past/concomitant medical history of the subjects, and to conduct detailed physical examinations, and measure vital signs (including heart rate, breathing, blood pressure, body temperature; to measure blood pressure in a resting state);
3. Laboratory testing:
 - 1) "Asia type" DEL typing;
 - 2) Cross-matching test (only for the "Asia type" DEL patients);
 - 3) Blood routine: white blood cells (WBC), neutrophils (NEUT), hemoglobin (Hb), hematocrit (Hct), platelets (PLT);
 - 4) Four items for infections detection;

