 - 5) Liver function testing: alanine aminotransferase (ALT), aspartate aminotransferase (AST), total bilirubin (TBIL), direct bilirubin (DBIL), total plasma protein (TP), plasma albumin (ALB);
 - 6) Renal function testing: Urea, creatinine (Cr);
 - 7) Examination of coagulation function: prothrombin time (PT), activated partial thromboplastin time (APTT), thrombin time (TT), fibrinogen (FIB);
 - 8) Urine routine;
 - 9) Stool routine, occult blood test;
 - 10) Pregnancy test: The women patients who reach menopause, or are undergoing menstruation at the time of the test, or have undergone birth control surgery do not need to have a pregnancy test, but need to record the reason for not doing so.
 - 11) Electrocardiogram.
4. Combined treatment/medication;
5. Evaluation of the patients for participation of this study based on inclusion and exclusion

criteria.

(II) Phase II of Visiting: Blood transfusion treatment period (0~1 days)

1. To record the detail of transfusion, including the time of transfusion start and end, the type of transfusion, the volume of transfusion, and to observe the adverse reaction during the transfusion treatment;
2. Observation of vital signs: temperature, heart rate, breathing, blood pressure;
3. Observation and recording of adverse events;
4. Combined treatment/medication.

(III) Phase III of Visiting: 1 day to 1 month after blood transfusion

1. Physical examination, observation of vital signs (including heart rate, breathing, blood pressure, body temperature and to measure blood pressure in a resting state);
2. Laboratory testing:
 - 1) Detection of anti-D immune response (using antibody screening test);
 - 2) Blood routine: including white blood cells (WBC), neutrophils (NEUT), hemoglobin (Hb), hematocrit (Hct), platelets (PLT);
3. Observation and recording of adverse events;
4. Combined treatment/medication.

(IV) Phase IV of Visiting: 1 month to 12 months after blood transfusion

1. Laboratory testing:
 - 1) Detection of anti-D immune response (using antibody screening test);
 - 2) "Asia type" DEL blood group typing.
2. Observation and recording of adverse events.

(V) Phase V of Visiting: Over 12 months after blood transfusion

1. Laboratory testing:
 - 1) Anti-D immune response test (using antibody screening test);
 - 2) "Asia type" DEL blood group typing.
2. Observation and recording of adverse events.

IX. Adverse events, serious adverse events

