8. Including the supervision date, time, the name of the supervisor, the problems found during the supervision and handling methods, etc.

(V) The inspection of clinical research

The clinical trial supervision and management department and the sponsor could authorize the auditors to carry out systematic inspection on the clinical study to determine whether the implementation of the trial is consistent with the trial scheme and whether the reported data is consistent with the records of all clinical participating institutes, that is, whether the data reported or recorded in the case report form is the same with the medical record or other original records. The audit shall be performed by the person not directly involved in the clinical study.

XI. Data management

(I) Data entry and modification

The leading institute of the trial is responsible for the data entry and management. For the questions in the case report form, the data manager will send the questions to the researcher through the supervisor, and the researcher shall answer and return them as soon as possible. The data manager will modify, confirm and input the data according to the researcher's answers, and send the DRQ again if necessary.

(II) Data locking

After all doubts are solved and the established database is confirmed to be correct, the data manager should write the data management audit report and lock the audited data. The locked data file and statistical plan will not be changed.

XII. Statistical analysis

(I) The population for statistical analysis

The population for analysis includes safety analysis set (SS) and full analysis set (FAS).

1. The Safety analysis population: the subjects receiving at least one time of blood transfusion.
2. Full analysis population.

(II) Statistical analysis method

1. Demographic data and baseline analysis

* Analysis according to FAS;

- * Descriptive demographic data and other baseline characteristic values;
- * To calculate the number of cases, mean value, standard deviation, median, minimum and maximum for the continuous variables;
- * To calculate the frequency for the count and grade data.

2. Safety analysis

The SS population was used for safety analysis, and safety indexes included adverse events, laboratory examination, vital signs, etc. To summarize the data by stages and units. The adverse events will be aggregated.

* Adverse events

All adverse events will be coded with MedDRA.

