According to NCI CTCAE V5.0, the incidence (frequency) and severity distribution of AE, TEAE, SAE and AESI were summarized according to SOC and PT in MedDRA code.

The subjects who terminated the treatment due to the adverse events, the subjects who had SAE and the dead subjects will be listed (at least including the start date, end date, severity, relationship with trial intervention, measures taken, outcome of AE).

* Laboratory examination

Blood routine and biochemical indexes were used to describe the measurement value and change value before and after treatment with mean \pm standard deviation, maximum value, minimum value and median. And the normal and abnormal changes before and after treatment were described with cross classification table.

Urine routine: use cross classification table to describe the normal and abnormal changes before and after treatment.

The proportion of the subjects with abnormal and clinically significant changes will be described, in which whether the abnormal has clinical significance is judged by the researchers.

The list of subjects with abnormal changes (with or without clinical significance) after treatment.

* ECG examination

Descriptive statistical ECG indicators compared with the baseline changes, using a cross classification table to describe the normal and abnormal changes before and after treatment, and a list of data will be provided.

* Vital signs, physical examination and other safety related examinations

The examination results of vital signs and changes compared with the baseline will be described statistically.

The subjects with abnormal changes in physical examination compared with baseline were described in the form of list.

(III) The software for analysis

SAS9.4 is used for the statistics analysis of the general data.

XIII. Preservation of the original data

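### Section XII plans before/after tables for biochemistry, urine and ECG, but no post-transfusion test is scheduled for any of them, and electrolytes are scheduled at no visit

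*Combined protocol and SAP*

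**What the plan says.** **Analysis text.** Section XII(II)2, Laboratory examination, states: "Blood routine and biochemical indexes were used to describe the measurement value and change value before and after treatment", and adds a normal/abnormal cross table. For urine: "Urine routine: use cross classification table to describe the normal and abnormal changes before and after treatment". For ECG: "Descriptive statistical ECG indicators compared with the baseline changes", again with a cross table. The same section promises the proportion of subjects with clinically significant abnormal changes. Vital signs are to be described as changes from baseline, and for physical examination: "The subjects with abnormal changes in physical examination compared with baseline were described in the form of list".

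**Evaluation indices.** Section VII(II), item 4, lists blood routine and then "renal function (Urea, Cr), liver function (ALT, AST, TBIL, DBIL, TP, ALB), electrolytes", all to be assessed before and after transfusion. It names no visit, and it does not mention urine or ECG.

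**Schedule.** Section VIII lists liver function, renal function, urine and ECG at Phase I, before transfusion. The laboratory tests after transfusion are the antibody screen and blood routine at Phase III, then the antibody screen and DEL typing at Phases IV and V. The flow chart in XV marks liver, renal, urine and ECG at Stage 1 only. Electrolytes appear in VI(III) and VII(II)4, but in no visit list of VIII and in no row of the flow chart.

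**The concern.** A before/after table needs a value on each side of the transfusion. If sites follow the visit schedule, the after column for biochemistry, urine and ECG is empty, or it is filled by whichever patients happened to be tested. Where tests were ordered for a reason, the means, change values and proportions would describe those patients and not the safety set. The denominator for the proportion with clinically significant changes would also be undefined, and an untested patient could be taken for one with no abnormal change.

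The trial has no control arm and its analysis is descriptive, so the laboratory safety evidence consists of these within-patient comparisons. A reader of the report needs to know who was measured.

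**Working it through.** No figure in the plan needs to be reproduced. The check sets each comparison in XII against the visit lists in VIII and the marks in XV.

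| Test group | Analysis in XII | Scheduled before transfusion | Scheduled after transfusion | Pair |
|---|---|---|---|---|
| Blood routine | values, change, cross table | Phase I | Phase III | yes |
| Vital signs | change from baseline | Phase I | Phases II and III | yes |
| Physical examination | list of abnormal changes | Phase I | Phase III (XV also Stages 4 and 5) | yes |
| Biochemistry: liver | values, change, cross table | Phase I | none | no |
| Biochemistry: renal | as liver | Phase I | none | no |
| Biochemistry: electrolytes | as liver | none | none | no |
| Urine | cross table | Phase I | none | no |
| ECG | change, cross table | Phase I | none | no |

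Counting biochemistry once, XII makes six baseline comparisons. Three have scheduled follow-up and three (biochemistry, urine, ECG) do not. For the three without, VIII and XV agree with each other, so a mark lost from the flow chart does not explain the gap.

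**Analytes in VII(II)4.** Blood routine 5 + renal 2 + liver 6 + electrolytes 5 = 18.

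- Scheduled before and after: 5/18 = 28% (blood routine only).
- Scheduled before only: (2 + 6)/18 = 8/18 = 44%.
- Scheduled at no visit: 5/18 = 28% (electrolytes).

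So all 2 + 6 + 5 = 13 biochemical analytes lack a scheduled post-transfusion value.

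**Other routes to a post-transfusion value.**

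- VI(III) lets the investigator decide on a repeat after an abnormality.
- Note a of the flow chart does the same for the rows it marks, which include liver, renal and ECG. It does not mark urine, and electrolytes have no row, so only the general rule in VI(III) can trigger a repeat of those two.
- IX(IV)1 requires a retest when a post-treatment blood, urine, stool, ECG, liver or kidney result is abnormal. It presupposes a first post-treatment test, which for all of these except blood routine the schedule does not provide.
- IX(IV)2 asks for a last laboratory examination for certain withdrawals and does not define its content.
- Usual care may supply results, but the plan sets no collection rule or window for them.

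None of these gives every transfused patient a value.

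**The case against.** The strongest reply is that little depends on these tables. The study is about anti-D alloimmunisation, the analysis is descriptive, and no decision rule uses biochemistry, urine or ECG. That is correct and limits the weight of the point.

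Second, patients in hospital may have routine tests after transfusion, and such results need not be selected by symptoms. This stands in part: the documents neither confirm nor exclude it, so the after column is possibly, not certainly, selected. It would still be incomplete to an unknown degree.

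Third, some protection is already planned. XII promises a list of subjects with abnormal changes and a data listing for ECG, and the abstract includes the number of cases among the summaries for continuous variables. This too stands in part. Those lists do not call for the number tested or the reason for testing, and the statement on case numbers does not cover the cross tables.

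Fourth, XII does not define its biochemical indexes, so equating them with the 13 analytes in VII(II)4 is an inference. The percentages show how far the schedule falls short of VII(II)4 and do not measure bias.

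Finally, VII(II)4 and IX(IV)1 suggest that post-transfusion testing was intended. That shows the sections contradict each other; it does not supply a visit.

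**Conclusion.** The concern holds. Three of the six baseline comparisons in XII cannot be produced for the safety set from the planned visits, and 13 of the 18 analytes in VII(II)4 have no scheduled post-transfusion value. The documents do not say whether the schedule or the index and analysis text governs.

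The consequence is limited to secondary safety tables. Anti-D, haemoglobin, haematocrit and vital signs have scheduled measurement after transfusion, and adverse events are recorded at every later stage. The count of 13 assumes that biochemistry in XII means the renal, liver and electrolyte analytes of VII(II)4. The finding for urine and ECG needs no such assumption. The plan should be corrected, but the main safety question is not at risk.

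**What to change.** Reconcile VII(II)4, VIII, XII and XV, with VI(III) and IX(IV)1 aligned to them. Do this before database lock, because XI(II) states: "The locked data file and statistical plan will not be changed". There are two ways, and the documents do not settle which was meant.

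**(a) Fit the analysis to the schedule.** Limit the before/after summaries to blood routine, vital signs and physical examination. Report liver, renal, urine and ECG at baseline only. List any unscheduled post-transfusion result with the number tested and the reason for testing, without means or proportions. Change VII(II)4 to match, including electrolytes. This is wording only and works even if collection is finished; the price is fewer laboratory safety statements.

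**(b) Fit the schedule to VII(II)4.** Add liver, renal and electrolyte tests at Phase III, where blood tests are already planned, and electrolytes at Phase I. State a window, since Phase III runs from one day to one month and change values would otherwise mix very different intervals. Urine and ECG comparisons would still be dropped or listed, and every table would show the number with a paired value. The cost is routine assays, presumably borne by the sponsor, since X(III) says related laboratory tests are free. Whether they can share an existing sample would have to be confirmed. Patients already past Phase III would gain nothing.

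Either way the protocol text changes, so the ethics committee must approve it.

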

[23] No.184 [2000]. *Technical Specifications for Clinical Blood Transfusion.*

[24] NMPA. *Technical Guidelines for Vaccine Clinical Trials* [20] 2004.12

[25] NMPA. *Management Practices for the Quality Control of Drug Clinical Trials* 2016.12

[26] NMPA. *Guiding Principles for Quality Management of Vaccine Clinical Trials (tentative standard)* 2013.1

XV. The flow chart of the Clinical research

	Stage 1	Stage 2	Stage 3	Stage 4	Stage 5
Visiting time	-7~ 0 Days before transfusion	Blood transfusion treatment period (0~1days)	1 day to 1 month after blood transfusion	1 month to 12 months after blood transfusion	Over 12 months after blood transfusion
Informed consent signed	●				
Basic information collection	●				
Physical examination	●		●	●	●
Vital signs	●	●	●		
Blood routine	●		●		
Urine routine	●				
Stool routine + Occult Blood ^{ab}	●				
Liver function ^a	●				
Renal function ^a	●				
Coagulation function ^a	●				
Four items for infections detection	●				
Electrocardiogram ^a	●				
HCG test ^b	●				
Genotyping of "Asia type" DEL	●			●	●
Detection of alloanti-D	●		●	●	●
Cross-matching test ^c	●				
Review of the inclusion and exclusion criteria	●				
Recording of adverse events		●	●	●	●

Recording of combined treatment	•	•	•	•	•
CRF reviewed by the person in charge					•
CRF reviewed by the inspector					•

Note: ^aIn case of any abnormality of the patients during the follow-up, the authorized investigator shall determine whether re-examination is necessary. If necessary, the investigator shall be instructed to make a timely return visit, record in detail, and follow-up to the normal or baseline level, or the investigator can reasonably explain the abnormality and think that no follow-up is necessary;

^bOptional, depending on the clinical situation;

^c “Asia type” DEL patients will be involved.
